## 11 STATISTICAL CONSIDERATIONS

### 11.1 Study Design and Objectives

This study is a prospective, baseline controlled, multi-center, one arm study. The purpose of this study is to evaluate the performance and safety of the BeShape One device for waist circumference reduction.

### 11.2 Study Endpoints

#### 11.2.1 Primary Endpoint

The primary endpoint is the change from baseline to 12 weeks after treatment in waist circumference.

#### 11.2.2 Secondary Endpoints

The secondary endpoints are

- Change from baseline to 6 weeks after treatment in waist circumference.
- Global Aesthetic Improvement scale at 6 weeks and 12 weeks following treatment measuring subject rated improvement.
- Satisfaction scale at 6 weeks and 12 weeks following treatment measuring subject rated satisfaction.
- Clinical Global Aesthetic Improvement scale at 6 weeks and 12 weeks following treatment measuring investigator rated improvement.
- Pain score after treatment measuring subject comfort/pain level.

### **11.2.3 Exploratory Endpoint**

Change from baseline to 6 weeks and 12 weeks after treatment of abdominal fat thickness.

### **11.2.4 Safety Endpoints**

The incidence, severity and type of adverse events recorded throughout the study and post treatment phase, including skin reactions (erythema, edema, irritation, etc.).

Safety will also be assessed with vital signs.

## **11.3 Statistical Hypothesis**

The null hypothesis of this study is that there is no difference between the mean decrease from baseline of waist circumference 12 weeks after treatment.

The alternative hypothesis is that there is a difference in the mean decrease from baseline of waist circumference 12 weeks after treatment.

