## 10 PATIENT COMPLETION / WITHDRAWAL

### 10.1 Completion

A subject will be considered to have completed the study if they complete the treatment as well as both follow up visits.

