### 10.2 Withdrawal from the study

A subject will be withdrawn from the study for any of the following reasons:

- Withdrawal of consent
- Subject is not compliant with requirements of the study, including inclusion and exclusion criteria.
- The investigator believes that for safety reasons (e.g. an adverse event) it is in the best interest of the patient to stop the study.
- The study is prematurely stopped or halted (e.g. clinical halt)

Subjects enrolled in the study can discontinue their participation at any time for any reason without prejudice or reduction in the quality of their medical care. The investigators or sponsor can terminate a subject's participation in this study to protect the subject's health or if the subject fails to follow directions resulting in noncompliance to study procedures. Subjects who fail to complete the study will be replaced and will not be considered evaluable.

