### **11.5.2 Full Analysis Set (FAS)**

The full analysis set (FAS) includes all eligible subjects who are enrolled in the study, received treatment and have at least one post treatment waist circumference measurement. The FAS will be used for the summary and analyses of the primary, secondary and exploratory endpoints.

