### **11.5.3 Per Protocol (PP) Analysis Set**

The per protocol (PP) analysis set will consist of all subjects from the FAS without any major protocol violations. The PP analysis set will be used for a sensitivity analysis of the primary endpoint.

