### **11.6.4 Efficacy Analyses**

All efficacy analyses will be performed on the FAS. All efficacy endpoints will be listed by subject and presented descriptively.

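### Section 11.3 sets up a hypothesis on week-12 waist change that the descriptive-only analysis in 11.6.4 cannot decide, and sections 10.2 and 11.5.2 disagree on who counts

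*Combined protocol and SAP*

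**What the plan says.** All references are to the combined protocol and SAP.

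- **Endpoint (11.2.1).** "The primary endpoint is the change from baseline to 12 weeks after treatment in waist circumference".
- **Hypothesis (11.3).** The null is that "there is no difference between the mean decrease from baseline of waist circumference 12 weeks after treatment"; the alternative is that "there is a difference in the mean decrease from baseline of waist circumference 12 weeks after treatment".
- **Efficacy method (11.6.4).** Analyses use the FAS, and "All efficacy endpoints will be listed by subject and presented descriptively". The section says nothing more about method.
- **Analysis sets (11.5.2, 11.5.3).** The FAS takes eligible enrolled subjects who "received treatment and have at least one post treatment waist circumference measurement". "The PP analysis set will be used for a sensitivity analysis of the primary endpoint", but no method is named for that or for the analysis it is meant to support.
- **Completion and replacement (10.1, 10.2).** "A subject will be considered to have completed the study if they complete the treatment as well as both follow up visits". "Subjects who fail to complete the study will be replaced and will not be considered evaluable".
- **Sample size (11.4).** 70 subjects, with no effect size, SD, alpha, power or dropout rate.

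**The concern.** A plan that states a null and an alternative commits itself to deciding between them. That needs a null value, a test or interval, an error rate and a direction. Section 11.3 supplies none of these. Its null speaks of no difference but names only one quantity, so the reader has to infer from the baseline-controlled design that the reference is zero. The alternative has no direction, although the synopsis and 5.1 frame the endpoint as a reduction; taken literally, a mean increase would also satisfy it.

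The study is open-label with one arm, and section 13.2 says its results will help determine whether the device is effective. Under the present text, the method, the sidedness and the set of subjects behind the primary figure could all be settled after the data are seen.

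The second problem is narrower. One part of the plan calls a non-completer non-evaluable, and another part may put the same person in the primary analysis set.

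**Working it through.** **1. Is a decision rule given elsewhere?** Section 11.5.2 speaks of analyses and 11.5.3 of a sensitivity analysis, but neither names a test, model or interval. The listed appendices cover the visit schedule and photography. Section 11.6.4 is intact, so this is not a redaction or extraction gap.

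**2. Can the test be inferred from the sample size?** No. The 70 in 11.4 has no inputs and can be neither reproduced nor refuted. By the one-sample normal formula n = ((z_alpha + z_power)/d)², with d = mean change / SD of change and no dropout, 70 corresponds to:

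| Assumed alpha | Assumed power | d |
|---|---|---|
| two-sided 5% | 80% | 0.335 |
| two-sided 5% | 90% | 0.387 |
| one-sided 5% | 80% | 0.297 |
| one-sided 5% | 90% | 0.350 |

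The number fits many designs and points to none of them.

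**3. What would 70 week-12 values support?** The 95% CI half-width is t(0.975, 69)/√70 = 1.9949/8.3666 = 0.238 SD. By the exact noncentral t, 80% power at two-sided 5% needs a mean change of 0.340 SD. The documents give no SD, so the values below are assumptions:

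| SD of change (assumed) | CI half-width | Mean change for 80% power |
|---|---|---|
| 2 cm | 0.48 cm | 0.68 cm |
| 3 cm | 0.72 cm | 1.02 cm |
| 4 cm | 0.95 cm | 1.36 cm |

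**4. Does the unstated choice matter?** A two-sided 5% test rejects when |mean|/SD is at least 0.238. A one-sided 5% test rejects at 1.6672/8.3666 = 0.199. An observed ratio of 0.22 gives t = 0.22 × 8.3666 = 1.841 on 69 df, so p = 0.070 two-sided and 0.035 one-sided. Between 0.199 and 0.238 (0.60 to 0.72 cm at SD 3 cm) the same reduction passes or fails according to a choice the plan does not make.

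**5. Who contributes to the week-12 mean?** The rules, applied to eligible treated subjects with a baseline value:

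| Waist values after treatment | 10.1 and 10.2 | 11.5.2 | Adds to observed week-12 mean? |
|---|---|---|---|
| weeks 6 and 12 | evaluable | in FAS | yes, under both |
| week 6 only | not evaluable | in FAS | no, under either |
| week 12 only | not evaluable | in FAS | yes under 11.5.2, no under 10.2 |
| neither | not evaluable | not in FAS | no, under either |

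Only the third row moves the observed mean. With n completers and k week-12-only subjects, the two versions differ by k/(n + k) times the difference between the two groups' mean changes. The documents give no basis for k or for that difference, so no figure in cm can be put on it.

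**The case against.** The strongest reply is that the study is simply descriptive. If mean, SD and n are reported, anyone can compute an interval. Section 13.2 promises only that the results will help with the question of effectiveness. A p-value against zero in one uncontrolled arm would not settle that question anyway. Much of this stands: the information is not lost, and an estimate with its CI and no p-value is a respectable plan. But section 11.3 then has no function and should go. While it stays, the plan lacks a rule fixed in advance.

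On the analysis set, it can be said that 11.5.2 and 11.6.4 both name the FAS, and that evaluability in 10.2 is not a defined analysis set and may govern only the replacement count. That reading is plausible, but the text does not say so. One sentence would settle it.

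A reader might also infer that the non-evaluable rule biases the primary estimate through dropouts who have week 6 only. The documents do not support that. Such subjects have no week-12 change and add nothing to a descriptive week-12 mean under either rule. Bias from missing week-12 values is a general risk that would arise under 11.5.2 alone, and it would affect a paired t-test equally. It does not measure the conflict between 10.2 and 11.5.2.

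**Conclusion.** The concern holds and should be fixed. Section 11.3 poses a hypothesis with no reference value, and nothing in the plan can decide it. The practical size is the band of observed mean/SD from 0.199 to 0.238, where the verdict at 5% turns on unstated sidedness. This assumes 70 week-12 values and a paired t-test; the cm figures also need an assumed SD. The conflict over who counts is real but confined, for the observed mean, to subjects with week 12 and no week 6.

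Two stronger conclusions are not supported. The documents do not show that 70 is the wrong number, only that it has no stated basis. Nor would adding a test make the trial evidence of a device effect, because a one-arm change from baseline does not by itself show one.

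**What to change.** By formal amendment (15.1), before outcome data are reviewed:

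1. **Section 11.3.** H0: mean change in waist circumference from baseline to week 12 = 0. H1: mean change is not 0. Two-sided alpha 0.05, with only a mean reduction counted as favourable. The alpha is this review's proposal, since the plan gives none.
2. **Section 11.6.4.** The primary analysis reports the mean week-12 change in FAS subjects with a week-12 value, the number contributing, a two-sided 95% CI and the paired t-test p-value. Repeat it on the PP set. As a sensitivity analysis for missing week-12 values, fit a likelihood-based repeated-measures model of weeks 6 and 12 to all FAS subjects; it assumes that missingness is explained by the observed data. Other efficacy endpoints stay descriptive.
3. **Section 10.2.** State that replacement does not remove from the FAS an eligible treated subject who has a post-treatment waist measurement.

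If a descriptive study is intended, delete 11.3 instead and report the same estimate with its 95% CI and no p-value; item 3 is still needed. In either case, state that a one-arm change from baseline does not by itself show a device effect. If outcome data have already been reviewed, label the test post hoc and rely on the estimate and its interval.

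The cost is two short paragraphs and one sentence, with no added visits or measurements. The sponsor gives up choosing the method after seeing the data, and the t-test omits subjects without a week-12 value.

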## **11.4 Sample Size Determination**

A total samples size of 70 subjects should be enrolled into the study.

## **11.5 Analysis Data Sets**

### **11.5.1 Safety Analysis Set**

All subjects who received treatment will be included in the safety analysis set. The safety analysis set will be used for the summary and analyses of all safety endpoints.

### **11.5.2 Full Analysis Set (FAS)**

The full analysis set (FAS) includes all eligible subjects who are enrolled in the study, received treatment and have at least one post treatment waist circumference measurement. The FAS will be used for the summary and analyses of the primary, secondary and exploratory endpoints.

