### 5.1 Primary Endpoint

To evaluate the reduction in waist circumference following BeShape treatment at the final follow-up visit compared to baseline.

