## **7 STUDY DESIGN**

This study is a prospective, baseline controlled, multi-center, one arm clinical study aimed to assess the efficacy and safety of the BeShape One™ device for waist circumference reduction.

All subjects will undergo an assessment of their general health. A single treatment utilizing the BeShape One™ device will be administered.

During the follow-up period, visits will be conducted as follows: 6 weeks (6wk FU), and 12 weeks (12wk FU) post treatment. Subject's waist circumference will be measured at baseline (before treatment) and at each of the follow up visits. Circumference reduction will be assessed at each post baseline visit. Additionally, investigator and subject assessments will be completed at each follow up visit. Photography of the treatment areas will be performed under visible light conditions of the front, right, left and back view of the subjects at the baseline visit (before first treatment) and at the last follow-up visit (12wk FU).

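### The full analysis set admits subjects seen only at week 6, but the week-12 primary result, followed as written, is a mean over week-12 completers labelled as FAS

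*Combined protocol and SAP*

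**What the plan says.** - **Who is in the set.** Section 11.5.2 takes eligible, enrolled subjects who "received treatment and have at least one post treatment waist circumference measurement", and states: "The FAS will be used for the summary and analyses of the primary, secondary and exploratory endpoints".
- **When waist is measured.** Section 7 schedules follow-up at "6 weeks (6wk FU), and 12 weeks (12wk FU) post treatment" and has no other post-treatment waist measurement.
- **What is estimated.** Section 11.2.1: "The primary endpoint is the change from baseline to 12 weeks after treatment in waist circumference". The alternative hypothesis in 11.3 uses the same time point: "there is a difference in the mean decrease from baseline of waist circumference 12 weeks after treatment". Section 5.1 gives no week number: "To evaluate the reduction in waist circumference following BeShape treatment at the final follow-up visit compared to baseline".
- **How it is analysed.** Section 11.6.4: "All efficacy endpoints will be listed by subject and presented descriptively". No model, test, interval or imputation rule is given.
- **What happens to non-completers.** Section 10.1 defines completion as the treatment plus both follow-up visits. Section 10.2 has non-completers replaced and regarded as not evaluable. The analysis-set definitions in 11.5 do not use the term evaluable.
- **Sensitivity analysis.** The only one is the per-protocol set in 11.5.3: FAS members without a major protocol violation.

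**The concern.** A treated subject who attends week 6 and misses week 12 belongs to the FAS but has no value for the primary endpoint. A descriptive summary leaves that subject out of the mean while the table heading still counts them. Section 10.2 goes further and sets the subject aside altogether. On either route the primary result describes those who came back at week 12.

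This is harmless if coming back is unrelated to response. In a cosmetic study, someone who sees little change at week 6 may have less reason to return. That is plausible, but the documents do not show it. With one open-label arm there is no control group in which similar loss could partly cancel, so any selection goes straight into the headline reduction.

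**Working it through.** **1. Following a week-6-only subject through the plan.**

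- Under 11.5.2 the subject is in the FAS.
- Under 11.2.1 the subject has no primary endpoint value.
- Under 11.6.4 nothing replaces that value, so the mean is taken over observed week-12 changes.
- Under 10.1 and 10.2 the subject is a non-completer, is replaced and is not evaluable, which contradicts the first step.
- Under 11.5.3 the per-protocol set can only remove FAS members. It cannot restore a missing week-12 value.

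**2. What replacement does.** The target of 70 in 11.4 has no derivation, so there is no planned loss rate to reproduce. Suppose 5% to 20% are lost and replacement continues until 70 complete. The number treated is then 70/0.95 = 73.7, so 74, up to 70/0.80 = 87.5, so 88. Replacement restores the number of week-12 values. It leaves the bias alone, because the replacements who complete are selected in the same way.

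**3. Simple arithmetic (assumed inputs).** Of 70 treated, m lack week 12 and c = 70 - m have it. Let the true reduction in those lost be f times that in completers. The relative overstatement is 70/(c + m f) - 1.

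- m = 4 (about 5%): f = 0.5 gives 70/68 - 1 = 2.9%; f = 0 gives 70/66 - 1 = 6.1%.
- m = 14 (20%): f = 0.5 gives 70/63 - 1 = 11.1%; f = 0 gives 70/56 - 1 = 25.0%.

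**4. Simulation (assumed inputs).** 70 subjects; true mean change -1.5 cm at week 6 and -2.5 cm at week 12; SD 3 cm; correlation 0.7; normal changes. Loss at week 12 follows a logistic model in the week-6 change, with the slope given per SD.

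| Loss model | Missing week 12 | Completers' mean (cm) | Overstatement (cm) |
|---|---|---|---|
| Unrelated to response | 13% to 24% | about -2.50 | none |
| Mild, slope 0.5 | 5% to 10% | -2.55 to -2.61 | 0.05 to 0.11 |
| Stronger, slope 1 | 13% to 24% | -2.73 to -2.93 | 0.23 to 0.43 |

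A steeper slope of 1.5 at 13% to 24% missing takes the overstatement to about 0.3 to 0.6 cm.

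The mechanism is simple. The bias equals correlation x SD x the amount, in SD units, by which completers' mean week-6 change differs from everyone's. Here 0.7 x 3 = 2.1 cm per SD, so overstatements of 0.05 and 0.43 cm correspond to completers doing better at week 6 by 0.05/2.1 = 0.02 SD and 0.43/2.1 = 0.20 SD.

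**5. Set against precision.** The standard error of the mean is 3/√66 = 0.37 cm with 4 missing and 3/√53 = 0.41 cm with 17 missing (24%). The bias therefore runs from a small fraction of a standard error to about one.

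**6. What the alternatives return.** A likelihood estimate using both visits gave -2.49 to -2.50 cm under loss dependent on the week-6 change. Setting missing changes to zero gives (1 - proportion missing) x completers' mean: 0.90 x -2.60 = -2.34 cm in the mild case at 10%, and 0.76 x -2.93 = -2.23 cm in the stronger case at 24%.

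**The case against.** **Carry-forward.** Because 5.1 says only "at the final follow-up visit compared to baseline", a reader might infer that each subject's last attended visit counts, so that week 6 would stand in for a missing week 12. The documents do not support this. The synopsis attaches 12 weeks to the final visit, Section 7 identifies the last follow-up visit as the 12-week one, and 11.2.1 and 11.3 both fix 12 weeks. No passage plans carry-forward. The 5.1 wording is merely loose.

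**Size.** With one treatment and two follow-up visits over 12 weeks, loss may well be low. At 5% to 10% missing with mild selection, the bias is at most about 0.11 cm against a standard error near 0.37 to 0.38 cm. This stands: the documents do not allow anyone to say that the result will be materially biased, only that the plan could neither prevent nor show it.

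**The model's good showing.** The likelihood estimate is unbiased in the simulation because loss was made to depend only on the observed week-6 change, the condition under which the method works. It would not fully correct loss driven by the unseen week-12 value, and it does not recover treated subjects with no post-treatment reading, who are outside the FAS. This also stands, and it is why a conservative sensitivity analysis and a count of missing values belong beside the model.

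**Proportion.** The plan is a descriptive single-arm summary, and a repeated-measures model is one option among several. That is fair as to the model's details. It does not excuse the absence of any rule for a missing primary value, or the conflict between 10.2 and 11.5.2.

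**Conclusion.** The point holds. The FAS definition, the week-12 endpoint, the descriptive method and the replacement rule together give a completers' mean presented as an FAS result, and the one planned sensitivity analysis cannot detect selective loss. The conflict between 10.2 and 11.5.2 is in the text and rests on no assumption.

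The size is conditional: no bias if loss is unrelated to response, and otherwise the overstatements tabulated above. These figures rest on assumed means, SD, correlation and loss, none of which the documents supply. This should be corrected before the data are seen. It does not invalidate the study.

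**What to change.** - **11.6.4:** estimate the mean week-12 change in the FAS, with a 95% confidence interval, from a repeated-measures model of the week-6 and week-12 changes. Include visit and baseline waist (centred, so that the week-12 term is the FAS mean), with unstructured covariance; site is optional. State that the estimate is valid if loss depends only on observed values.
- **Sensitivity analysis:** add one conservative analysis that sets missing week-12 changes to zero.
- **Reporting:** give the number of treated subjects and the number of FAS subjects without a week-12 value.
- **10.2 and 11.5.2:** reconcile them so that treated non-completers with a post-treatment reading stay in the FAS analysis even if further subjects are enrolled.
- **5.1:** name week 12, in line with the synopsis and 11.2.1. This is tidying only.

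Cost: an amendment to the wording and a few lines of code, with no new visits or data. The headline may be slightly less favourable than the completers' mean.

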## **8 ADMINISTRATION OF TREATMENT**

Subjects will receive one treatment with the BeShape One™ device on the anterior abdomen. Prior to the treatment, measurements of weight and waist circumference will be performed.

Before starting the procedure using the BeShape One™ device, the administrator should clean the entire treatment area with a wet wipe and hairs should be shaved. Conductive castor oil will be applied to the treatment areas to ensure full contact between the applicator and the skin. Prior to treatment, it is necessary for the operator to ensure that all treatment areas are in close contact with the cup-shaped applicator chamber. Following visual confirmation of proper contact with the tissue, the skin will be marked as a

treatment area using a skin marking pen. Subjects will receive treatment on at least 4 abdomen/flanks treatment areas and up to 6 treatment areas, at the discretion of the investigator. During the procedure, subjects will lie in the supine position in order to provide the best access to the treatment area.

Upon completion of treatment, the treated area will be freed from the applicator. The administrator should check for any immediate skin reaction and record any outstanding findings on the CRF before proceeding to the next area of treatment.

Immediately after completion of the procedure (after all treatment areas have been treated), the following evaluations and measurements will be performed:

- \* Assessment of adverse events, including any skin reaction (erythema, edema, irritation, etc.) or any other side effects;
- \* Pain assessment.

All findings will be recorded on the Adverse Events form.

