## **9 STUDY PROCEDURES**

### **9.1 Overview**

Patient visits may occur within a  $\pm$  2 days deviation from the scheduled time.

Efficacy rating scales to be used in the study include:

- Waist circumference measurement
- Abdominal fat thickness measurements
- Global Aesthetic Improvement scale (GAI)
- Clinical Global Aesthetic Improvement scale (CGAI)

Safety evaluations will include a pain scale and adverse event monitoring throughout the study. Number, severity and type of adverse events will be recorded throughout treatment and follow-up phases.

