### **9.6.4 Pain Rating Scale**

The subjects will rate their pain at the treatment visit.

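### The treatment-day pain score is assigned to the FAS, so treated subjects who never return for a waist measurement, or are found ineligible, drop out of the pain summary

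*Combined protocol and SAP*

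**What the plan says.** Section 11.2.2 lists among the secondary endpoints: "Pain score after treatment measuring subject comfort/pain level". Section 5.2 and the synopsis agree. On timing, section 9.6.4 says: "The subjects will rate their pain at the treatment visit".

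Section 11.5.2 then assigns the analysis set: "The FAS will be used for the summary and analyses of the primary, secondary and exploratory endpoints". No exception is made for pain. The same section says that the FAS "includes all eligible subjects who are enrolled in the study, received treatment and have at least one post treatment waist circumference measurement". Section 7 says that "waist circumference will be measured at baseline (before treatment) and at each of the follow up visits", and the follow-up visits are at 6 and 12 weeks. Section 8 schedules only adverse event and pain assessments immediately after the procedure.

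Other sections bear on the same score:

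- Section 9.1 omits pain from its list of efficacy scales and says: "Safety evaluations will include a pain scale and adverse event monitoring throughout the study".
- Sections 5.4 and 11.2.4 define the safety endpoints through adverse events, and 11.2.4 adds vital signs. Neither lists the pain score.
- Section 11.5.1 puts all treated subjects in the Safety Analysis Set and uses that set for the safety endpoints.
- Section 10.2 says: "Subjects who fail to complete the study will be replaced and will not be considered evaluable".
- Section 8 says of the immediate post-procedure assessments: "All findings will be recorded on the Adverse Events form".

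**The concern.** The pain score is a tolerability result that is complete on day 0. Whether it counts should not depend on something that happens, or is discovered, later. Under 11.5.2 it depends on two such things: the subject attending a visit six weeks later, and the subject's eligibility being upheld.

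If early loss is related to how the treatment felt, the FAS summary describes a selected group. Subjects who stayed away because treatment hurt would be missing from the table that reports how much it hurt. The reverse is also possible, and the documents give no dropout rate or reasons from which to judge. In a single-arm study reported descriptively, the summary is itself the result, so its denominator matters. Section 4 compares competing methods partly on pain, so this figure is likely to be read as part of the case for the device.

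**Working it through.** **Step 1: who can enter the FAS, and when.**

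| Item | Source | Content |
|---|---|---|
| Endpoint class of pain | 5.2, 11.2.2 | secondary |
| Time of pain score | 8, 9.6.4 | treatment visit (day 0) |
| Set for secondary endpoints | 11.5.2 | FAS |
| FAS conditions | 11.5.2 | eligible, enrolled, treated, one or more waist values after treatment |
| Waist measurements | 7 | before treatment, week 6, week 12 |
| Set holding all treated subjects | 11.5.1 | Safety, used for safety endpoints |
| Safety endpoints | 5.4, 11.2.4 | adverse events; vital signs (11.2.4) |

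The first waist value that can qualify a subject for the FAS is at week 6. A subject treated on day 0 with a pain score but no later visit is in the Safety Analysis Set and outside the FAS. So is a treated subject later judged ineligible. No section places the pain score on the Safety Analysis Set.

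**Step 2: size.** The plan has no figure to reproduce: section 11.4 gives 70 subjects with no dropout allowance, and no pain-scale range is stated. The values below are assumptions for illustration, on an assumed 0-10 scale.

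Let N be the number treated, k the number of them outside the FAS, m the FAS mean pain, and d the mean of those outside minus m. Then

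all-treated mean = [(N − k)·m + k·(m + d)] / N = m + k·d/N,

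so the FAS mean is too low by k·d/N, or too high if d is negative.

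*Without replacement, N = 70:*

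| k | share omitted, k/70 | d = −2 | d = 0 | d = 2 | d = 4 |
|---|---|---|---|---|---|
| 2 | 2.9% | −0.06 | 0 | 0.06 | 0.11 |
| 4 | 5.7% | −0.11 | 0 | 0.11 | 0.23 |
| 7 | 10.0% | −0.20 | 0 | 0.20 | 0.40 |

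*With replacement as section 10.2 states, N = 70 + k (70 stayers plus k leavers):*

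| k | share omitted, k/(70 + k) | d = −2 | d = 0 | d = 2 | d = 4 |
|---|---|---|---|---|---|
| 2 | 2/72 = 2.8% | −0.06 | 0 | 4/72 = 0.06 | 8/72 = 0.11 |
| 4 | 4/74 = 5.4% | −0.11 | 0 | 8/74 = 0.11 | 16/74 = 0.22 |
| 7 | 7/77 = 9.1% | −0.18 | 0 | 14/77 = 0.18 | 28/77 = 0.36 |

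The d = 4 column corresponds, for example, to stayers averaging 4 and leavers averaging 8. The formula is the same whether a subject is outside the FAS through early loss or through ineligibility.

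**The case against.** Four points can fairly be made for leaving the plan as it is.

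1. *The plan can be read the other way.* Section 9.1 treats pain as safety, 11.6.4 applies the FAS to efficacy analyses, and 11.6.5 puts safety analyses on the Safety population. A programmer could follow that route and use all treated subjects. But 11.5.2 names secondary endpoints outright, and 11.6.5 speaks only of adverse events and vital signs. At best there are two readings with different denominators, which still needs settling.

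2. *Safety information is already covered.* Section 8 sends the immediate findings to the Adverse Events form, so pain or skin injury recorded as an adverse event is reported for every treated subject. This stands, and it limits the point to the summary of the score.

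3. *The effect is small and hypothetical.* This also stands. The analysis is descriptive, no decision rule uses it, and the sign of any bias is unknown. The largest shift shown, 0.40, needs 10% early loss, no replacement and a 4-point difference; nothing in the documents suggests that combination.

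4. *Ineligible subjects should be rare.* Eligibility is checked before treatment, so this route needs a screening error. That is fair; early loss is the more plausible route, although section 10.2 does provide for withdrawing subjects who do not meet the entry criteria.

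None of these removes the mismatch. Together they make it a modest correction.

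**Conclusion.** The concern holds. Followed as written, the plan discards day-0 pain scores from treated subjects because of later non-attendance or a later eligibility finding, and this sits badly with section 9.1. That conclusion rests on the text alone.

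The size cannot be determined from the documents. Under the assumed inputs, the error in mean pain is zero if leavers resemble stayers, and about 0.06 to 0.20 points in either direction for a 2-point difference with 2 to 7 early leavers. For a 4-point difference it reaches 0.40 without replacement, or 0.36 with it. The primary endpoint and adverse event reporting are unaffected. The change is worth making because it is cheap and gives the tolerability result one clear denominator.

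**What to change.** Make short edits in four sections:

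- **11.5.1 and 11.6.5**, add: *The post-treatment pain score is summarised on the Safety Analysis Set, using all treated subjects with a recorded score; the number of missing scores is reported.*
- **11.5.2**, after the word secondary in the sentence on use of the FAS, insert: *(except the pain score)*.
- **10.2**, add: *Non-evaluable status under this section does not remove a treated subject from the Safety Analysis Set or from the pain summary.* This partly repeats 11.5.1 but prevents a wider reading of 10.2.

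Pain can remain a secondary endpoint. A cross-reference to the pain score in 11.2.4 would complete the alignment with 9.1 but is not needed for the change to work.

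No new data are collected. The pain table will have a different denominator from the other secondary endpoints and needs a footnote. The edits cannot recover scores that were never taken: section 8 places the pain assessment after all areas have been treated, so a subject who stops part-way may have none. That is why the count of missing scores should be shown.
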